## 5. PARTICIPANT SELECTION

### 5.1 Inclusion Criteria

- Patients must provide informed written consent.
- Patients must be  $\geq 18$  years of age.
- ECOG performance status 0-1.
- Clinical stage IV (metastatic) ER, PR, HER2 negative invasive mammary carcinoma, previously documented by histological analysis and that meets the following criteria:
  - HER2 negativity is defined as any of the following by local laboratory assessment: In-situ hybridization (ISH) non-amplified (ratio of HER2 to CEP17  $< 2.0$  or single probe average HER2 gene copy number  $< 4$  signals/cell), or IHC 0 or IHC 1+ (if more than one test result is available and not all results meet the inclusion criterion definition, all results should be discussed with the Protocol Chair to establish eligibility of the patient)

- ER and PR negativity are defined as  $\leq 10\%$  of cells expressing hormonal receptors via IHC analysis.
- Willing to undergo biopsy of a metastatic lesion (in patients with reasonably accessible metastatic lesions such as chest wall, skin, subcutaneous tissue, lymph nodes, bones, peripheral lung, and liver metastases).
- Measurable disease, defined as at least one lesion that can be accurately measured in at least one dimension by RECIST criteria v1.1.
- Zero or one prior chemotherapy regimens for metastatic disease.
- No prior treatment with carboplatin in the metastatic setting. Carboplatin in neoadjuvant/adjuvant setting may be allowed if prior treatment with carboplatin was completed at least one year prior to initiation of this study and after discussion with the study chair.
- Patients must have adequate hematologic, hepatic, and renal function. All tests must be obtained less than 28 days from initiation of study drug (C1D1). This includes:
  - $ANC \geq 1000/mm^3$
  - Platelet count  $\geq 100,000/mm^3$
  - Calculated creatinine clearance  $\geq 30$  mL/min using the Cockcroft and Gault Formula (see Section 10.2)
  - Bilirubin, SGOT, SGPT, alkaline phosphatase  $\leq 2.5x$  upper limits of normal if no liver metastases present. Serum total bilirubin must be  $\leq 3x$  upper limits of normal for patients with Gilbert disease. Total bilirubin, SGOT, SGPT  $\leq 5x$  upper limits of normal if liver metastases present.

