- History of idiopathic pulmonary fibrosis (including pneumonitis), drug-induced pneumonitis, organizing pneumonia (i.e., bronchiolitis obliterans, cryptogenic organizing pneumonia), or evidence of active pneumonitis on screening chest CT scan. History of radiation pneumonitis in the radiation field (fibrosis) is permitted.
- Positive test for HIV (testing required prior to registration)
- Active hepatitis B (defined as having a positive hepatitis B surface antigen [HBsAg] test at screening) or hepatitis C
- Patients with past hepatitis B virus (HBV) infection or resolved HBV infection (defined as having a negative HBsAg test and a positive antibody to hepatitis B core antigen [anti-HBc] antibody test) are eligible.
- Patients positive for hepatitis C virus (HCV) antibody are eligible only if polymerase chain reaction (PCR) is negative for HCV RNA.
- Active tuberculosis
- Receipt of a live, attenuated vaccine within 4 weeks prior to initiation of study drug (C1D1) or anticipation that such a live, attenuated vaccine will be required during the study
- Prior treatment with CD137 agonists, anti-PD-1, or anti-PD-L1 therapeutic antibody or pathway-targeting agents
- Treatment with systemic immunostimulatory agents (including but not limited to interferons or IL-2) within 4 weeks or five half-lives of the drug (whichever is shorter) prior to randomization
- Treatment with systemic corticosteroids or other systemic immunosuppressive medications (including but not limited to prednisone, dexamethasone, cyclophosphamide, azathioprine, methotrexate, thalidomide, and anti-tumor necrosis factor [TNF] agents) within 2 weeks prior to cycle 1, day 1, or anticipated requirement for systemic immunosuppressive medications during the trial. Patients who have received acute, low-dose, systemic immunosuppressant medications (e.g., a one-time dose of dexamethasone for nausea) may be enrolled in the study. Patients on a stable low dose ( $\leq 10$  mg) daily prednisone or equivalent are allowed on study. Patients with a history of allergic reaction to IV contrast requiring steroid pre-treatment should have baseline and subsequent tumor assessments performed using MRI. The use of inhaled corticosteroids for chronic obstructive pulmonary disease, mineralocorticoids (e.g., fludrocortisone) for patients with orthostatic hypotension, and low-dose supplemental corticosteroids for adrenocortical insufficiency are

allowed.

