Upon satisfactory review of eligibility documents submitted, the Coordinating Center will approve enrollment and issue a subject ID number if one was not issued at screening. Once registration/enrollment confirmation from Coordinating Center is received, the site may proceed with protocol procedures.

Please contact the assigned Study Contact with any questions regarding this process. You can also reach out to your assigned CRA once the study is activated.

The VICC Coordinating Center will assign sequence numbers to all patients in screening. Only patients deemed eligible will be randomized to a treatment arm. Sequence numbers will only be re-used if a patient screen fails and then re-screens. The Coordinating Center will randomize eligible patients to carboplatin + atezolizumab or carboplatin alone. Following registration and randomization, eligible participants should begin protocol treatment within 1 week. Issues that would cause treatment delays should be discussed with the Protocol Chair. If a participant does not receive protocol therapy following randomization within allowed time period, the participant will become ineligible and will not be enrolled on study. Such patients will have to undergo screening again to participate in the study in the future. Any requests for eligibility exceptions and/or deviations must be approved in writing by the Protocol Chair, as well as any committees required by local

institutional policies. As is generally accepted, standard of care procedures performed prior to consent, but within the protocol defined screening window for each assessment can be used for study purposes. All research only procedures must be performed after the consent date.

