- b Screening must occur within 28 days of dosing. The following procedures must be repeated at the day 1 visit if they were previously done  $>7$  days prior to study treatment administration: Medical and cancer history, physical examination, weight measurement, vital signs, hematology, serum chemistry panel. Tumor assessments must be repeated at the baseline visit only if determined to be changed by clinical exam or other clinical observations. SOC procedures performed prior to consent but within the protocol defined screening window for each assessment can be used for study purposes. All research only procedures must be performed after the consent date.
- c See section 10.1.2 for vital sign information during atezolizumab infusion.
- d The 30-day follow-up assessments should be done 30 ( $\pm$ 3 days) days after the last dose of study drugs. 30 day follow-up can be done by phone or by a clinic visit. Any ongoing toxicities should be documented. Any ongoing serious adverse events will be followed every 3 months (in person or by phone) until resolution. Any AEs or SAEs considered possibly or probably related to IMP that have not stabilized, returned to baseline, or are considered irreversible will continue to be monitored as per the protocol.
- e The physical examination will include measurements of height and weight at screening. Weight will be measured on day 1 of each cycle and at the End-of-treatment visit. Dosing changes are only required if the weight changes 10% or more. Physical examination will include examination of major body systems including neurologic, cardiac, respiratory, gastrointestinal, and skin. Clinically relevant signs and symptoms will be reported as AEs.

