- f Clinical laboratory tests will include hematology and serum chemistry panel including white blood cell count, differential, hemoglobin, platelet count, sodium, potassium, chloride, bicarbonate, BUN, creatinine, glucose, calcium, and magnesium, AST (SGOT), ALT (SGPT), and total serum bilirubin, albumin, and total protein. Additional tests will be performed when clinically appropriate. In case of Grade 3 or higher AST/ALT, additional testing will be done weekly until recovery to baseline value (see protocol section 9.1.2 and 9.2.2.1). Labs do not have to be repeated on cycle 1, day 1 if they were done up to 7 days prior to day 1. For all other timepoints, labs can be performed up to 3 days prior to each timepoint indicated in the study calendar. **Results from labs obtained on CID1 (up to -7 days) must meet eligibility criteria. At the start of each cycle, the ANC must be  $\geq 1000/\text{mm}^3$  and the platelet count must be  $\geq 80,000/\text{mm}^3$  (see section 9.2.1) for carboplatin to be administered. Atezolizumab may be administered if these criteria are not met at the discretion of the treating physician. Serum pregnancy test does not need to be performed for patients  $\geq 55$  years old, those who are known to be post-menopausal, or who have had a hysterectomy.**
- g Thyroid function studies: see section 9.1.4 for abnormal results
- h All patients will be tested for HIV and HIV-positive patients will be excluded from the clinical trial. Please note that this result must be back by the time patient starts study so it is advised this be drawn prior to day 1 if the result may take some time to obtain. HBV serology includes Hepatitis B surface antigen, anti-HBc, and anti-HBs. As above, it is advised the HBV serology be obtained in advance if results may be delayed. Hepatitis B virus (HBV) DNA must be collected on or before Cycle 1, Day 1 in patients who have negative serology for hepatitis B surface antigen and positive serology for anti-HBc.

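### Screening labs more than 7 days old at Day 1 can trigger a second eligibility judgement after open-label randomisation, and the timing of viral results relative to randomisation is inconsistent

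*Combined protocol and SAP*

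**What the plan says.** **Before randomisation.** Section 5.1 states for the hematologic, hepatic and renal criteria: "All tests must be obtained less than 28 days from initiation of study drug (C1D1". Section 6.1 states: "Only patients deemed eligible will be randomized to a treatment arm". It continues: "Following registration and randomization, eligible participants should begin protocol treatment within 1 week". A randomised patient who does not receive therapy in the allowed time is declared ineligible, is not counted as enrolled, and must be screened again to take part later.

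**At Day 1.** Footnote b of the Section 7.1 calendar says "The following procedures must be repeated at the day 1 visit if they were previously done" more than 7 days before treatment, and lists hematology and serum chemistry among them. Footnote f gives the matching exemption, "Labs do not have to be repeated on cycle 1, day 1 if they were done up to 7 days prior to day 1", and then the requirement "Results from labs obtained on CID1 (up to -7 days) must meet eligibility criteria". The next sentence of footnote f sets separate limits for giving carboplatin at the start of each cycle.

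**Viral tests.** Section 5.2 excludes from registration a patient with a "Positive test for HIV (testing required prior to registration". Footnote h says of the HIV result: "Please note that this result must be back by the time patient starts study". It advises, without requiring, that HIV and HBV blood be drawn ahead of Day 1 if results may be slow.

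**Analysis sets.** Section 8.1 describes an open-label trial. Section 8.7 labels as intent-to-treat, for the evaluation of response, the patients who start protocol treatment. Sections 17.1 and 17.2 do not name the population for the primary PFS comparison.

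**The concern.** Eligibility should be settled before the arm is assigned. Here the calendar can call for a second judgement against the entry criteria up to a week after assignment, when site and patient both know the arm. Whether to repeat a borderline test, wait a few days, ask for an exception or let the patient go can then depend on that knowledge. Such losses need not be balanced between arms. A treated-only analysis set would not show them, because the patients who were lost are not in it.

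The viral tests raise a smaller question of order. If a site follows footnote h rather than Section 5.2, an excluding result could first be seen after randomisation.

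**Working it through.** **1. Can a patient pass, be randomised, and then fail?** An illustrative timeline:

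| Day | Event | Rule |
|---|---|---|
| -20 | Platelets at or above 100,000/mm³ | 5.1 entry limit met; test under 28 days old |
| -5 | Randomised, arm known | 6.1; treatment due within 1 week |
| 1 | Panel more than 7 days old, so repeated | 7.1, footnote b |
| 1 | Platelets 95,000/mm³ | 7.1, footnote f: entry criteria not met |

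The same count of 95,000 satisfies the cycle-start limit of 80,000 in footnote f and Section 9.3.1. The footnote f eligibility sentence is therefore a different test from the cycle-start rule. It also brings in the Section 5.1 renal and hepatic limits, which the cycle-start rule does not mention.

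**2. Who is exposed?** Two conditions must both hold: the screening panel is more than 7 days old at Day 1, and the repeat is drawn after randomisation. A panel drawn on day -6 with randomisation on day -2 stands without repeat.

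**3. How does a failing patient leave the analysis?** Footnote f states no consequence. Removal comes through the late-start sentence in Section 6.1, and then through Section 8.7, which counts only patients who start treatment.

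**4. Viral results.** Section 5.2 puts HIV testing before registration, and Section 6.1 requires every criterion on the checklist to be met for registration. Footnote h sets a later deadline for the result. Section 5.2 says testing, not result, so the two can be read differently. Active hepatitis B is an exclusion defined by a screening test, but no passage says that its result must be in hand before randomisation.

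**5. Size, starting from the plan's own figure.** Inputs from Section 17.2: medians of 2.9 and 4.4 months, one-sided alpha 0.10, 80% power, 24 months' accrual, 12 months' further follow-up, 1:1 allocation. PFS is assumed exponential with uniform accrual.

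- Hazard ratio = 2.9/4.4 = 0.659; |ln HR| = 0.417.
- Events (Schoenfeld) = 4 × (1.2816 + 0.8416)² / 0.417² = 104 after rounding up.
- Event probability = 1 − [exp(−12λ) − exp(−36λ)] / (24λ), with λ = ln 2/median: 0.990 for control, 0.961 for the combination, mean 0.976.
- N = 104/0.976 = 106.6, which reproduces the stated 106. Expected events at 106 are 103.4.
- Power = Φ(√(events/4) × 0.417 − 1.2816) = 79.9% at 106.

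The documents give no rate of failure on the repeat panel, so the loss rates below are assumptions:

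| Share of 106 lost | Patients left | Expected events | Power |
|---|---|---|---|
| 0% | 106 | 103.4 | 79.9% |
| 2% | 103.9 | 101.3 | 79.3% |
| 5% | 100.7 | 98.2 | 78.4% |

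These percentages apply to all 106 patients. If only a fraction of patients has an older panel, a given failure rate among them produces a proportionally smaller loss.

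**The case against.** **The exposure is narrow.** Footnote f accepts panels from the 7 days before Day 1, and Section 6.1 expects registration documents 24-48 hours before the planned start, so many patients may need no repeat after randomisation. This stands. A reader might infer that every patient is re-tested after randomisation; the documents do not support that.

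**The HIV wording is loose, not permissive.** Section 5.2 makes HIV a bar to registration, the calendar lists viral serology only under screening, and Section 6.1 has the Coordinating Center review eligibility documents before approving enrolment. This also stands. A reader might infer that footnote h authorises randomisation with an HIV result pending. It does not; it conflicts with the other passages and has to be reconciled with them.

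**The bias runs through the late-start rule and the analysis set.** This is correct. Footnote f removes nobody by itself, and analysing all randomised patients by arm would end the exclusion. The calendar still matters, because it creates eligibility failures after randomisation that earlier testing could prevent.

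**Section 17.5 already covers ineligible patients.** It asks that all patients included in the study be assessed for response even if ineligible. However, Section 6.1 says that those not treated in time are not enrolled, so this does not clearly reach them. Section 17.5 also limits its main clinical benefit analysis to eligible patients with 4 weeks of drug.

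**Conclusion.** For patients whose blood counts and chemistry are more than 7 days old at Day 1 and are repeated after randomisation, the plan allows eligibility to be judged again with the arm known. A failure followed by no timely treatment removes the patient under Section 6.1 and leaves them out of the Section 8.7 set. The point does not extend to panels drawn before randomisation and within 7 days of Day 1. The viral-test point is an inconsistency in timing, not a rule allowing late results.

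This should not be read as a power problem. Even if 5% of all 106 patients were lost, power would fall by about 1.5 percentage points (79.9% to 78.4%). What matters is possible selection by known arm, whose size cannot be estimated because the documents give neither a failure rate nor the share of patients with older panels. The change is worth making because it costs little and closes a visible route to selective loss.

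**What to change.** 1. **Section 6.1 and the Section 7.1 calendar:** require the panel that decides eligibility to be drawn within 7 days before randomisation and reviewed by the Coordinating Center before the arm is assigned.
2. **Footnote h:** align it with Sections 5.2 and 6.1, so that HIV, HBV and HCV results are available before randomisation.
3. **Sections 6.1, 8.7 and 17:** state that the primary PFS analysis includes every randomised patient by assigned arm, including any who fail Day 1 labs or are never treated.
4. **Footnote f:** the sponsor should reconcile the Cycle 1 Day 1 eligibility sentence with the cycle-start limits and with Section 5.1. Which limits govern the first dose is a clinical decision on which I take no position.

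Item 1 makes late failures rarer but does not abolish them. A panel drawn 7 days before randomisation, with treatment 7 days after it, is 14 days old at dosing, and footnote b would still require a repeat. Item 3 deals with those cases.

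The cost is amendment wording, panels booked a few days earlier at some sites, and a second panel when dosing falls more than 7 days after the first. Keeping untreated randomised patients in the PFS analysis also means continuing to collect their progression and survival status.

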## 1. SCHEMA

\* Optional cross-over at progression

Tumor Assessment every 9 weeks

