## 2. STUDY DESIGN/SUMMARY

The primary objective of this phase II multiple institution trial is to evaluate the efficacy of carboplatin + atezolizumab versus carboplatin alone in patients with metastatic triple negative breast cancer. Patients with an ECOG performance status of 0-1 who have received either zero or one prior regimen for metastatic disease are eligible. Patients will be randomized to one of two arms. In arm 1, patients will receive combination therapy with carboplatin and atezolizumab and in arm 2 patients will receive carboplatin monotherapy. All patients will undergo core biopsy of a metastatic lesion (if reasonably safe) at baseline and at the time of progression. If a fresh biopsy is deemed not safe, a paraffin block from a prior biopsy or surgery must be available for enrollment. Standard staging radiology scans will be performed at baseline and every 9 weeks thereafter. Upon progression of disease (clinically or by RECIST), patients on the carboplatin alone arm may cross over to arm 1 to receive atezolizumab. All patients with progression of disease who want to cross over to receive atezolizumab are required to undergo a biopsy of a metastatic site at progression if reasonably safe. Patients who were receiving carboplatin + atezolizumab will be discontinued from study medications upon disease progression by RECIST. Patients will be screened and enrolled from the oncology practice at the Vanderbilt-Ingram Cancer Center and from participating member centers of the Translational Breast Cancer Research Consortium (TBCRC).

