- i Tumor assessment should be performed approximately every 3 cycles (up to -5 days) while on study treatment (i.e. on or up to 5 days prior to Day 1 of Cycles 4, 7, 10 etc) and at End-of-treatment visit if not obtained within the past 6 weeks. Scans should consist of CT scan of the chest, abdomen, and pelvis and a bone scan at baseline. Of note, if the prior bone scan did not show metastases, it does not need to be repeated if the bone scan was obtained within 8 weeks of CID1. Subsequent scans should consist of CT chest, abdomen and pelvis, and bone scan if bone metastases were present on the baseline studies. MRI is also an acceptable form of imaging. At the end of treatment, all scans (baseline and through disease progression) should be sent on a CD to the Vanderbilt Cancer Imaging Support Laboratory for central review and assessment. See Section 12.6 for details and address.
- j Archived tumor biopsy specimen: Archived biopsy block (unstained slides) will be requested at the time of registration prior to initiation of treatment. See Section 11.1 for details. If archived tissue is not available, the VICC coordinating center should be contacted.
- k After signing consent, a fresh tumor biopsy from a metastatic site amenable to a reasonably safe biopsy will be obtained prior to day 1 and upon progression of disease (see Section 11). The second biopsy will not be required for patients who are removed from study for reasons other than disease progression. A patient who undergoes a research biopsy procedure for the purpose of this protocol, in whom inadequate tissue is obtained, is not obligated to undergo a repeat biopsy.

- l After cycle 6, at the discretion of the treating physician, carboplatin can be stopped and atezolizumab can be continued as a single agent.
- m The dose of steroids before each carboplatin injection should be recorded. Prohibited medications (section 8) must be discontinued at least 7 days prior to initiation of study drug (C1D1).
- n 1, 2, and 3 year follow-up can be done by phone or chart review to document survival status, and if applicable, the date of death and cause of death. Surveillance for Adverse Events of Special Interest (AESIs) (see section 13.5.12) should be included.
- o Biopsy questionnaire should be filled out by the patient on C2D1. Form can be found in the packet of supplemental forms.  

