## 9.2 General Guidelines for Dosage Modification and Treatment Interruption or Discontinuation

Atezolizumab treatment will be given as long as the patient continues to experience clinical benefit in the opinion of the investigator until the earlier of unacceptable toxicity, symptomatic deterioration attributed to disease progression, or any of the other reasons for treatment discontinuation listed above.

There will be no dose reduction for atezolizumab in this study. **Patients may temporarily suspend study treatment for up to 84 days beyond the scheduled date of delayed infusion if study drug-related toxicity requiring dose suspension is experienced.** If atezolizumab is held because of AEs for > 84 days beyond the scheduled date of infusion, the patient will be discontinued from atezolizumab and will be followed for safety and efficacy as specified in the protocol.

If a patient must be tapered off steroids used to treat AEs, atezolizumab may be held for additional time beyond 84 days from the scheduled dose until steroids are discontinued or reduced to a prednisone dose (or dose equivalent) of  $\leq 10$  mg/day. The acceptable length of interruption will be at the discretion of the investigator.

Dose interruptions for reasons other than toxicity, such as surgical procedures, may be allowed. The acceptable length of interruption will be at the discretion of the Protocol Chair.

Patients should be assessed clinically (including review of laboratory values) for toxicity prior to, during, and after each infusion. If unmanageable toxicity due to atezolizumab occurs at any time during the study, treatment with atezolizumab should be discontinued.

Management of hepatitis/transaminitis, colitis, rash, and hypothyroidism are presented in this section as they have been observed in this study and are potentially immune related.

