##### 9.3.1.1 Carboplatin Dose Modification for Hematologic Toxicities

Toxicity	Carboplatin Dose
ANC $< 500/\text{mm}^3$ and platelets $\geq 50,000/\text{mm}^3$	Decrease AUC by 1
Platelets $< 50,000/\text{mm}^3$ , regardless of ANC	Decrease AUC by 1
Platelets $< 50,000/\text{mm}^3$ with Grade $\geq 2$ bleeding, regardless of ANC	Decrease AUC by 2
ANC $< 1000/\text{mm}^3$ plus fever of $\geq 38.5^\circ\text{C}$	Decrease AUC by 1

All dose reductions for the first episode of neutropenic fever or thrombocytopenia (platelet count  $< 25,000$  or  $< 50,000$  with bleeding or that requires transfusion) are permanent. If a second episode of neutropenic fever or thrombocytopenia requiring dose reduction occurs, the dose of carboplatin will be reduced according to physician judgment and local standard practice. Colony-stimulating factors, such as granulocyte colony-stimulating factor, may be used instead of dose reduction for neutropenic fever or Grade 4 neutropenia, according to the local standard practice and ASCO guideline. Patients who require a third dose reduction will immediately discontinue chemotherapy.

In the event that dose adjustments are needed for both ANC and platelets, patients are to receive the lower dose.

**For Grade 3 ANC toxicity** (ANC  $< 1000-500/\text{ml}$ ), carboplatin should be withheld until the patient recovers completely or to Grade 1 toxicity. The treatment should then be resumed at 50% dose (permanent dose reduction). If recovery to Grade 1 toxicity does not occur within 3 weeks, the patient's chemotherapy will be discontinued.

Treatment with carboplatin can be delayed for up to 3 weeks until the Day 1 ANC is  $\geq 1000/\text{mm}^3$  and the platelet count is  $\geq 80,000/\text{mm}^3$ . However, if the counts have not recovered in 3 weeks, the patient's chemotherapy will be dose-reduced, held until adequate neutrophil recovery, or

discontinued, according to physician judgment and local standard practice. If chemotherapy is held longer than 42 days, all study treatment should be discontinued.

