## **12. MEASUREMENT OF EFFECT**

For the purposes of this study, patients should be re-evaluated for response after every 3 cycles. Response and progression will be evaluated in this study using the international criteria proposed by the revised Response Evaluation Criteria in Solid Tumors (RECIST) Committee (version 1.1). Any evaluable or measurable disease must be documented at screening and reassessed at each subsequent tumor evaluation. For PFS analysis, patients will be considered to have disease progression if their tumor assessment shows PD by RECIST. However, as conventional response

criteria may not adequately assess the activity of immunotherapeutic agents because radiographic progressive disease does not necessarily reflect therapeutic failure, for patients on the carboplatin + atezolizumab arm, if a patient is found to have disease progression by RECIST, at the discretion of the treating physician, the patient may remain on study and managed by irRECIST (see section 12.5) provided he/she meets the following criteria:

- Evidence of clinical benefit as assessed by the investigator.
- Absence of symptoms and signs (including worsening laboratory values [e.g., new or worsening hypercalcemia]) indicating clinically significant progression of disease
- No decline in ECOG performance status that can be attributed to disease progression
- Absence of tumor progression at critical anatomical sites (e.g., leptomeningeal disease) and no other signs/symptoms of unequivocal disease progression. This includes tumor progression that cannot be managed by protocol-allowed medical interventions (ie., pain secondary to disease or unmanageable ascites, etc.), as determined by the investigator after an integrated review of radiographic data and clinical status.

Scans should be repeated after 6 weeks, and if progression is confirmed by irRECIST, the patient should be removed from study. If scans by irRECIST show the patient to not have disease progression, the patient may remain on study after discussion with the Protocol Chair. Patients on the carboplatin alone arm who show progression by RECIST must either be removed from study or cross over to receive atezolizumab.

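### Scans are tied to treatment cycles although the design states every 9 weeks, so unequal dose delays between arms can shift recorded PFS

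*Combined protocol and SAP*

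**What the plan says.** Two places set a calendar schedule. The Section 1 schema reads "Tumor Assessment every 9 weeks", and Section 2 reads "Standard staging radiology scans will be performed at baseline and every 9 weeks thereafter".

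The operative instructions set a cycle schedule. Section 7.1, footnote i, reads "Tumor assessment should be performed approximately every 3 cycles (up to -5 days) while on study treatment" and fixes the visit as "on or up to 5 days prior to Day 1 of Cycles 4, 7, 10 etc". The tumor assessment row of the Section 7.1 table also counts in cycles. Section 12 (repeated in the duplicated pages at the end of the document) reads "patients should be re-evaluated for response after every 3 cycles". Section 8.7 uses the same interval for patients who go on with one drug after toxicity to the other.

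The plan expects delays:

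- Section 9.3.1.1, on low counts: "Treatment with carboplatin can be delayed for up to 3 weeks until the Day 1 ANC is" at or above the threshold. Chemotherapy holds have a 42-day limit, and after a hold the schedule resumes in its usual order.
- Section 7.1, footnote f, when counts are too low for carboplatin: "Atezolizumab may be administered if these criteria are not met at the discretion of the treating physician".
- Section 9.2, on drug-related toxicity: "Patients may temporarily suspend study treatment for up to 84 days beyond the scheduled date of delayed infusion".

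For PFS, Section 12 counts progression when a tumor assessment shows PD by RECIST. Section 17 has no rule for late or unequally spaced assessments.

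**The concern.** Progression is seen only when someone looks, so the recorded PFS time is largely the date of the first scan after true progression. If scan dates follow cycles, a delay in dosing lengthens recorded PFS with no change in the disease.

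That would matter little if both arms slipped alike, but the rules allow them to slip differently. With low counts, a control cycle has no drug to give and waits. A combination patient with the same counts may receive atezolizumab on time, so the cycle and its scan can stay on schedule. In the other direction, an atezolizumab hold can arise only in the combination arm during randomized treatment. It can stop the cycle count mainly once carboplatin has stopped, which is allowed after cycle 6 or for toxicity.

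At stake is the primary comparison. The target gain is 1.5 months, about 6.5 weeks, which is less than one scan interval. Many events therefore fall on a few scan dates, and a shift of 1-3 weeks in one arm changes the order of events that the log-rank test uses.

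**Working it through.** **1. The design figure.** Inputs from Sections 17.1 and 17.2: medians 2.9 and 4.4 months, one-sided alpha 0.10, power 80%, 1:1 allocation, accrual 24 months, follow-up 12 months. With exponential PFS, HR = 2.9/4.4 = 0.659.

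- Schoenfeld events: 4(1.2816 + 0.8416)²/(ln 0.659)² = 18.03/0.1738 = 103.8, so 104.
- Event probability: 1 − exp(−12λ)(1 − exp(−24λ))/(24λ), with λ = ln 2/median. This gives 0.990 (control) and 0.961 (combination), mean 0.976.
- N = 104/0.9755 = 106.6. At N = 106, power is 79.9%.

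The stated 106 is reproduced.

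**2. When the two schedules part.** 3 × 21 days = 63 days = 9 weeks, so they agree if no cycle is late. At 4.35 weeks per month:

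- A 3-week delay before Cycle 4 moves the first scan from week 9 to week 12. That is 3/4.35 = 0.69 months, or 0.69/1.5 = 46% of the target gain.
- A 12-week (84-day) suspension of the cycle would move it to week 21. That is 12/4.35 = 2.8 months, more than the target gain.

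**3. Effect on the test.** Simulation with 53 per arm and exponential PFS; scans every third cycle, up to 5 days before Day 1; progression dated at the first scan after it occurs; one-sided 0.10 log-rank; 3,000 to 5,000 trials per scenario. Each delayed cycle slips by 1-3 weeks. The delay probabilities are assumptions.

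Power, medians 2.9 vs 4.4 months:

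| Control cycles delayed | Combination cycles delayed | Power |
|---|---|---|
| 0% | 0% | about 0.78 |
| 20% | 15% | about 0.76 |
| 20% | 10% | about 0.73 |
| 20% | 0% | about 0.69 |

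Type I error, median 2.9 months in both arms:

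| Control | Combination | When delays occur | Type I error |
|---|---|---|---|
| 0% | 0% | none | 0.10 |
| 20% | 20% | all cycles | 0.10 |
| 0% | 20% | after cycle 6 only (run from cycle 8) | about 0.14 |
| 0% | 20% | all cycles | about 0.20 |
| 10% | 20% | after cycle 6 only (run from cycle 8) | about 0.11 |
| 10% | 20% | all cycles | about 0.15 |

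Monte Carlo error is about 0.01; repeat runs agreed within about 0.02.

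**4. A second set of assumptions.** Here 20% or 40% of whole 9-week intervals are lengthened by a fixed 1 or 3 weeks (5,000 trials). Delays in the combination arm only give type I error of 0.155 to 0.272. Delays in the control arm only give power of 0.61 to 0.72. Equal delays give type I error of 0.094 to 0.103 and power of about 0.78. The pattern is the same.

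**The case against.** The strongest reply is that the arms share most of what causes delay. Both receive the same carboplatin dose on the same 21-day cycle, with the same count thresholds and with growth factor permitted. Giving atezolizumab alone when counts are low is left to the physician, and the plan does not say how such a cycle is numbered. A contrast as wide as 20% against 0% is therefore an extreme, and at 20% against 15% the loss of power is about 0.01 to 0.02. This stands, and it limits the likely size.

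A reader might infer that the combination arm will show a false gain, with type I error near 0.20. The documents do not support that. The figure needs combination-only delays from cycle 1, while Section 8.7 lets a patient with atezolizumab toxicity continue carboplatin alone, so early cycles can proceed. The clearer route, holds after carboplatin has stopped, gives about 0.14 even at 20% against 0%. Section 9.2 speaks of suspending study treatment, which could be read as both drugs, but it does not say so. The two mechanisms also act in opposite directions and may partly cancel.

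There is some mitigation: footnote i says approximately, visits have a 3-day window, and an end-of-treatment scan is required if none was done in the past 6 weeks. None of these keeps a scan on the calendar while treatment is on hold. Central review rereads the same scans and cannot recover a date on which no scan was made.

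**Conclusion.** The point holds as a contradiction between the stated 9-week schedule and the cycle-based instructions, with a conditional risk to the primary comparison. It would be too strong to say that any dose delay postpones the PFS event. A carboplatin-only delay in the combination arm need not move the cycle, deaths are not postponed, and what moves is the recorded radiographic date.

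Bias requires unequal delays. Its direction cannot be known from the documents: more delay in control costs power, and more delay in the combination raises type I error. Under the assumed rates, power lies between about 0.69 and 0.76 instead of 0.78, or type I error between about 0.11 and 0.20 instead of 0.10. These ranges rest on exponential PFS, 1-3 week delays and delay rates that the plan does not give. The sample size of 106 is not in question. This is a cheap improvement to a primary endpoint that is otherwise open to an avoidable bias.

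**What to change.** Reconcile the passages. State in the tumor assessment row of the Section 7.1 table, footnote i, Section 8.7 and Section 12 (both copies) that, during randomized treatment, tumor assessments in both arms take place every 9 weeks (63 days). Count from one fixed origin, randomization or Cycle 1 Day 1, regardless of dose delays, holds or cycle number, and keep the existing window. Dosing rules stay as they are.

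Add to Section 17 an interval-censored sensitivity analysis of PFS, using the last progression-free scan and the first scan showing progression. It also covers patients already scanned by cycle. Do not move progressions back to the nominal visit: a progression found at week 12 could then be dated to week 9, before it occurred.

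The cost is a short amendment. Some scans will no longer fall on Day 1 of a cycle, and a patient with delays may occasionally have one more scan than under the cycle schedule, still at the planned 9-week frequency.
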